**Prospective Randomized comparison Of prosthetic Valve Effective
orifice area: One-year analysis of two bovine PERIcardial valves
(PROVE-PERI trial)**

NCT 03796442

Trial Protocol v 1.4

Updated Dec 28, 2018

Statistical Analysis Plan

1. Inclusion criteria

- ① Patients who are scheduled to undergo AVR
- ② Over 19 years of age
- ③ Patients who are planned to receive a bioprosthetic valve for aortic valve substitute
- ④ Patients who or whose legal representative fill out a written consent form before the start of the clinical trial and patients who can comply with the clinical trial requirements

2. Exclusion criteria

- ① Patients with concomitant mitral or tricuspid valve operation
- ② Patients with severe left ventricular dysfunction (ejection fraction < 0.30)
- ③ Patients with infective endocarditis
- ④ Patients with a medical history such as a malignant disease that might limit the possibility of mid-term follow-up
- ⑤ Patients who refused study enrollment

3. Sample size calculation

The study is designed to have 80% power to detect 1-year AVMPG of $12.6 \pm 4.3 \text{ mmHg}$ for the study prosthesis [1] and $11.9 \pm 4.3 \text{ mmHg}$ for the control prosthesis, [2] with a 1-sided type I error of 2.5% and a noninferiority margin of 3mmHg. The noninferiority margin was determined by the values of 15mmHg for AVMPG of clinically significant aortic stenosis [3] and 12mmHg for AVMPG of the control prosthesis. Fifty-six patients in each group were needed to complete the study cohort. Allowing for a 20% dropout rate during the 1-year follow-up, we determined that the recruitment of 70 patients in each group was necessary.

- (1) Level of significance (α) = 0.025
- (2) Type II error (β) = 0.20, power of the test = 80%
- (3) Drop out rate = 20%
- (4) One-tailed test

H_0 (null hypothesis): $\mu_1 - \mu_2 \geq \delta$

H_1 (alternative hypothesis): $\mu_1 - \mu_2 < \delta$

(μ_1 : mean AVMPG of the study group on 1 – year echocardiographic follow – up ,
 μ_2 : mean AVMPG of the control group on 1 – year echocardiographic follow – up
 δ : noninferiority margin)

The calculation was performed using PASS Software(Power Analysis and sample size software: <http://www.ncss.com>), and the calculated formula is as follows.

$$n = \frac{(Z_\alpha + Z_\beta)^2 (\sigma_1^2 + \sigma_2^2)}{(\mu_1 - \mu_2) - \delta}^2$$

μ_1 = mean AVMPG of the study group on 1 – year echocardiographic follow – up

μ_2 = mean AVMPG of the control group on 1 – year echocardiographic follow – up

σ_1 = standard deviation of AVMPG of the study group on 1 – year echocardiographic follow – up

σ_2 = standard deviation of AVMPG of the control group on 1 – year echocardiographic follow – up

δ : noninferiority margin

※ Primary clinical endpoint

mean pressure gradient across the aortic valve (AVMPG) on 1-year echocardiographic follow-up

※ Secondary clinical endpoint

the effective orifice area (EOA) on 1-year echocardiographic follow-up

operative mortality, operative morbidities

1-year clinical outcomes (all-cause mortality, cardiac death and major adverse events)

The primary endpoint of the PROVE-PERI trial is AVMPG on 1-year echocardiographic follow-up. The secondary endpoints are the EOA on 1-year echocardiographic follow-up and 1-year clinical outcomes including all-cause mortality, cardiac death and MAEs.

The study is designed to have 80% power to detect 1-year AVMPG of 12.6 ± 4.3 mmHg for the study prosthesis [2] and 11.9 ± 4.3 mmHg for the control prosthesis, [4-6] with a 1-sided type I error of 2.5% and a noninferiority margin of 3mmHg. The noninferiority margin is determined by the values of 15mmHg for AVMPG of clinically significant aortic stenosis [7] and 12mmHg for AVMPG of the control prosthesis. Fifty-six patients in each group are needed to complete the study cohort. Allowing for a 20% dropout rate during the 1-year follow-up, we determine that the recruitment of 70 patients in

each group was necessary.

Statistical analyses will be performed using SPSS software (version 25.0; IBM, Armonk, NY) and SAS software (version 9.3; SAS Institute, Cary, NC). Data will be expressed as the mean \pm standard deviation, median with IQRs or proportions. Comparisons between the 2 groups will be made using the chi-square test and Fisher's exact test for categorical variables and Student's t-test or the Mann-Whitney test for continuous variables, as appropriate. The null hypothesis is that the AvaluTM is inferior to the CEPME based on the AVMPG at 1-year echocardiographic follow-up, with a non-inferiority margin of 3mmHg. The result for the primary endpoint is presented with 97.5% one-sided confidence interval for mean difference between groups. The non-inferiority test will be performed using a t-test which compares mean difference between groups with the non-inferiority margin under the one-sided significance level of 0.025. For analysis of 1-year clinical outcomes including all-cause mortality, cardiac death, and MAEs, events will be counted at postoperative 1 year, and comparisons between the 2 groups will be made using the chi-square test and Fisher's exact test. A P value of $< .050$ will be considered statistically significant. All outcomes will be compared with an intention-to-treat base. Per-protocol and as-treated analyses will be added for hemodynamic outcomes.

References

3. D Rennie. How to report randomized controlled trials. The CONSORT statement. *JAMA.* 1996;276:649.
4. Fiegl K, Deutsch MA, Rondak IC, Lange R, Guenzinger R. Matched Comparison of Two Different Biological Prostheses for Complete Supra-annular Aortic Valve Replacement. *Thorac Cardiovasc Surg.*

2015;63:459-66.

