Surgeries are performed under median sternotomy or upper partial sternotomy under cardiopulmonary bypass with cold cardioplegic arrest. After the diseased AV is excised, the annulus is prepared for landing the prosthesis, and the proper valve sizes for both types of

prostheses are decided before randomization. Then, randomization is performed with a web-based block randomization method with randomly determined block sizes of 4 and 6. After randomization, the assigned prosthesis is implanted with non-everting transverse mattress sutures. The knot-tying is performed manually or by using an automated knot-fastener.

Patients are evaluated with early clinical outcomes and early echocardiographic measurements. After discharge, all patients undergo regular postoperative follow-up through the outpatient clinic at 3- to 6-month intervals and are interviewed by telephone for confirmation of their condition if the last clinic visit has not been conducted as scheduled. At postoperative 1-year, clinical outcomes and echocardiographic measurements are evaluated as scheduled.

※ Randomization : Patients who meet the inclusion criteria and the exclusion criteria are randomly assigned to 1 of the 2 bioprostheses in a 1:1 manner. Randomization is performed with a web-based block randomization method (<https://mrcc.snuh.org/>) with randomly determined block sizes of 4 and 6, considering the institution as a stratification factor.

2) Outcome measures

- 1) Demographics: age, sex, height, weight, BMI, BSA, diagnosis, operation name
- 2) Preoperative data
 - Risk factors: DM, HTN, smoking, dyslipidemia, stroke, COPD, CKD, chronic liver disease, coronary disease, peripheral vascular disease, history of cardiac surgery, New York Heart Association functional class, STS mortality risk, EuroSCORE II
 - Echocardiographic measurements: Effective orifice area, mean pressure gradient, peak pressure gradient, LA dimension, LV ejection fraction, LV end diastolic dimension, LV end systolic dimension, pulmonary artery systolic pressure, TR severity, etc.
 - Electrocardiography
 - Laboratory tests: CBC, routine chemistry, NT-proBNP, CRP, ABGA, lactate, PT, aPTT
 - CT scan (thoracoabdominal CT angio)
 - Pulmonary function test
- 3) Operative data: CPB time, ACC time, concomitant procedures, operative findings
- 4) Postoperative data

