 - Early clinical outcomes: op mortality, op morbidities (low cardiac output, bleeding reoperation, perioperative myocardial infarction, perioperative stroke, acute kidney injury, respiratory complications, postoperative atrial fibrillation, and mediastinitis)

- Echocardiographic measurements: Effective orifice area, mean pressure gradient, peak pressure gradient, LA dimension, LV ejection fraction, LV end diastolic dimension, LV end systolic dimension, pulmonary artery systolic pressure, TR severity, etc.
- Electrocardiography: 1st, 2nd and 3rd AV block, bundle branch block

5) 1-year follow-up data

- Clinical outcomes: all-cause mortality, cardiac death and major adverse events (valve-related mortality, structural valve deterioration, nonstructural dysfunction, thromboembolic and bleeding events, prosthetic valve endocarditis, AV reintervention or the need for a new permanent pacemaker or defibrillator within 14 days after the index operation), last follow-up date, New York Heart Association functional class
- Echocardiographic measurements: Effective orifice area, mean pressure gradient, peak pressure gradient, LA dimension, LV ejection fraction, LV end diastolic dimension, LV end systolic dimension, pulmonary artery systolic pressure, TR severity, etc.
- Electrocardiography: 1st, 2nd and 3rd AV block, bundle branch block

※ Primary clinical endpoint

mean pressure gradient across the aortic valve (AVMPG) on 1-year echocardiographic follow-up

※ Secondary clinical endpoint

the effective orifice area (EOA) on 1-year echocardiographic follow-up

operative mortality, operative morbidities

1-year clinical outcomes (all-cause mortality, cardiac death and major adverse events)

3) Differences from previous treatments and studies

When compared with previous treatments, the operative strategies and perioperative management are identical, but only the bioprostheses used in the treatments are different.

When compared with previous studies, all studies previously performed were prospective single-arm designs or retrospective studies. To the best of our knowledge, the present study is the first prospective randomized controlled trial comparing results of AVR using the Avaluus™ valve with those using another bovine pericardial valve that has been used worldwide.

4) Risks associated with the study

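### One-year EOA is compared without covariate adjustment and with no pre-specified confidence interval, although BSA is collected and randomisation is stratified by institution: a loss of precision only

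*SAP*

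**What the plan says.** The protocol (section 10, Outcome measures) and the SAP both list "the effective orifice area (EOA) on 1-year echocardiographic follow-up" as a secondary endpoint. Neither names an analysis for it. Protocol section 10, Efficacy, gives methods for the primary endpoint and for the 1-year clinical events, but not for EOA. The only rule that reaches EOA is in the SAP's closing paragraph on statistical analyses: "Student's t-test or the Mann-Whitney test for continuous variables, as appropriate". The same paragraph promises summary statistics by mean and SD or median and IQR, a confidence interval for the primary endpoint only, and per-protocol and as-treated analyses for haemodynamic outcomes. A P value below .050 "will be considered statistically significant"; sidedness is not stated.

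Three baseline quantities are relevant, all in protocol section 10:

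- BSA is a listed baseline item: "Demographics: age, sex, height, weight, BMI, BSA, diagnosis, operation name".
- Randomisation is in blocks, "considering the institution as a stratification factor".
- During surgery "the proper valve sizes for both types of" "prostheses are decided before randomization". Valve size is not named among the operative data items, and no common sizing scale is defined.

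**The concern.** EOA is an absolute area. It can be expected to vary with the size of the patient, although the documents do not say so and give no figure for it. Whatever part of that variation BSA or institution explains stays in the error term of an unadjusted two-group test. The result is a wider interval and lower power than the same patients could give.

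Reporting is a second, separate matter. The trial is sized for the mean pressure gradient (AVMPG), not for EOA. The SAP leaves the choice between the t-test and Mann-Whitney open, and Mann-Whitney gives no mean difference. Without a pre-specified interval, a non-significant EOA result will not show which differences the data exclude.

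**Working it through.** **Inputs.** From the documents: AVMPG 12.6 and 11.9 mmHg, SD 4.3, margin 3 mmHg, one-sided alpha 0.025, power 80%, 56 completers per arm, 20% dropout. Assumed: two-sided 0.05 for EOA; multiple correlation r of the covariates with EOA between 0 and 0.6.

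**Step 1: the plan's own sample size.** n = (1.960 + 0.842)² × (4.3² + 4.3²) / (0.7 − 3)² = 7.849 × 36.98 / 5.29 = 54.87, so 55 per arm by the normal formula. With the noncentral t distribution, power is 79.4% at 55 and 80.1% at 56. The plan's 56 is therefore the t-test answer, and 56 / 0.80 = 70. Both figures reproduce. No corresponding figure for EOA exists to check.

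**Step 2: what the unadjusted EOA comparison can do.** In units of the EOA SD, with 56 per arm:

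- SE = √(2/56) = 0.189
- 95% CI half-width = 1.960 × 0.189 = 0.370 SD
- difference detectable with 80% power = (1.960 + 0.842) × 0.189 = 0.529 SD

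**Step 3: effect of adjustment.** For p covariates and N = 112, the variance is multiplied by about f = (1 − r²) × (N − 3)/(N − 3 − p). The second term is the price of estimating the covariate effects. The equivalent unadjusted n per arm is 56/f, and the CI half-width is 0.370 × √f.

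Three covariates (BSA, institution and a common-scale size), with 109/106 = 1.028:

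| Assumed r | r² | f | Equivalent n per arm | CI half-width (SD) |
|---|---|---|---|---|
| 0 | 0 | 1.028 | 54 | 0.376 |
| 0.3 | 0.09 | 0.936 | 60 | 0.358 |
| 0.5 | 0.25 | 0.771 | 73 | 0.325 |
| 0.6 | 0.36 | 0.658 | 85 | 0.300 |

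Break-even is at f = 1, that is R² = 3/109 = 0.028.

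Two covariates (BSA and institution only), with 109/107 = 1.019: the equivalent n at the same r is 55, 60, 73 and 86, and the break-even R² is 2/109 = 0.018. Dropping valve size saves almost nothing in degrees of freedom. It matters only through whatever r it would have added.

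**Step 4: simulation check.** 4,000 trials per setting, 56 per arm, two covariates, true difference 0.529 SD. Unadjusted power was 79–81%. Adjusted power was 83%, 91% and 97% at R² = 0.1, 0.3 and 0.5. Type I error of the adjusted test was 4.5–5.0%.

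**The case against.** The strongest reply is that nothing here is an error. The unadjusted test is valid under randomisation, EOA is secondary, no power is claimed for it, and the same efficiency argument could be made for any continuous outcome. All of that stands, and it limits the point to an improvement.

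It also stands that the link between EOA and body size is not in the documents, so the gain is conditional on an assumed range.

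A reader might infer four stronger things that the documents do not support:

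- **That the EOA comparison is biased or the trial's conclusion weakened.** Randomisation protects the unadjusted comparison, and the primary test is on AVMPG.
- **That EOA deserves primary-level treatment because it is in the title** ("Prospective Randomized comparison Of prosthetic Valve Effective" opens it). Both documents make AVMPG primary and EOA secondary.
- **That the plan yields only a P value for EOA.** The SAP also promises group summaries. With arm means, SDs and numbers, an unadjusted interval could be worked out. The accurate statement is that no interval for the EOA difference is pre-specified. The documents plan no claim that EOA is equal.
- **That pre-randomisation valve size is already in hand.** The protocol says that the sizes are decided, not that they are recorded, and it describes one size for each prosthesis type.

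Finally, an unadjusted CI would by itself settle the reporting matter. Adjustment rests on the precision argument alone.

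**Conclusion.** The point holds as a minor, low-cost improvement. BSA is a listed baseline item and institution is the stratification factor, so a more precise analysis of the same endpoint is available without new patients. With three covariates, the equivalent sample size runs from about 54 per arm if they explain nothing to about 85 at r = 0.6. These figures assume 56 completers per arm, a two-sided 5% level, linear covariate effects and the stated range of r. For BSA and institution alone the r could lie at the low end of that range; the documents do not allow it to be narrowed. The potential loss is about 1–2 patients per arm, so the balance favours adjustment once R² exceeds roughly 0.02 to 0.03.

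**What to change.** In the SAP, give 1-year EOA its own sentence: a linear model on treatment, BSA and institution, reporting the adjusted mean difference with a 95% CI, with the unadjusted comparison kept as a sensitivity analysis.

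Add pre-randomisation valve size as a covariate only if it is recorded for every patient on one common scale, for example the size chosen for the control prosthesis in both arms. Do not adjust for the implanted label size. It depends on the arm, and adjusting for it could remove part of the device effect.

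The core change costs SAP wording only. Including valve size may also need a data-collection item, since it is not among the listed operative data. The statistical downside is a negligible loss of precision if the covariates explain almost nothing.

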The study is designed to have 80% power to detect 1-year AVMPG of 12.6 ± 4.3 mmHg for the study prosthesis [2] and 11.9 ± 4.3 mmHg for the control prosthesis, [3-5] with a 1-sided type I error of 2.5% and a noninferiority margin of 3 mmHg. The noninferiority margin is determined by the values of 15 mmHg for AVMPG of clinically significant aortic stenosis [6] and 12 mmHg for AVMPG of the control prosthesis. Fifty-six patients in each group are needed to complete the study cohort. Allowing for a 20% dropout rate during the 1-year follow-up, we determine that the recruitment of 70 patients in each group is necessary.

- (1) Level of significance (α) = 0.025
- (2) Type II error (β) = 0.20, power of the test = 80%
- (3) Drop out rate = 20%
- (4) One-tailed test

H_0 (null hypothesis): $\mu_1 - \mu_2 \geq \delta$

H_1 (alternative hypothesis): $\mu_1 - \mu_2 < \delta$

(μ_1 : mean AVMPG of the study group on 1 – year echocardiographic follow – up ,

μ_2 : mean AVMPG of the control group on 1 – year echocardiographic follow – up

δ : noninferiority margin)

The calculation was performed using PASS Software(Power Analysis and sample size software: <http://www.ncss.com>), and the calculated formula is as follows.

$$n = \frac{(Z_\alpha + Z_\beta)^2 (\sigma_1^2 + \sigma_2^2)}{((\mu_1 - \mu_2) - \delta)^2}$$

μ_1 = mean AVMPG of the study group on 1 – year echocardiographic follow – up

μ_2 = mean AVMPG of the control group on 1 – year echocardiographic follow – up

σ_1 = standard deviation of AVMPG of the study group on 1 – year echocardiographic follow – up

σ_2 = standard deviation of AVMPG of the control group on 1 – year echocardiographic follow – up

δ : noninferiority margin

4) Subject recruitment plan

Subject recruitment will be performed for the patients who are scheduled to undergo AVR and who are hospitalized at Seoul National University Hospital and Seoul National University Bundang Hospital after providing sufficient explanation and informed consents. The subjects will be recruited competitively.

10. Methods

1) Detailed process of the study

Patients over 19 years of age who are scheduled to undergo AVR on a nonemergency basis and who are planned to undergo primary AVR using stented bioprostheses at 2 institutions are assessed for eligibility for study enrollment. After excluding the patients who meet the exclusion criteria and who refuse to participate, enrolled patients are randomly assigned to 1 of the 2 bioprostheses in a 1:1 manner.

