*** Predicted risks**

Because both prostheses have proved their efficacy and safety by prospective pivotal trials

and many related studies, the predicted risks associated with the present study will be comparable to routinely performed aortic valve replacement.

If any adverse event or risk occurs, providing the standard management for them will be sufficient.

5) Criteria for suspension and dropout

Patients who decline to participate in the trial are suspended or drop-out

6) Safety

Safety outcomes will be a composite of death from any cause and individual major postoperative complications including low cardiac output, bleeding reoperation, perioperative myocardial infarction, perioperative stroke, acute kidney injury, respiratory complications, postoperative atrial fibrillation, and mediastinitis.

All safety outcome measures will be assessed and recorded at designated time intervals by research personnel at each individual center. Data regarding every event will be reviewed and adjudicated centrally by the principal investigator and sub-investigator.

7) Efficacy

Efficacy analysis will be performed for ITT(Intention to treat) group, and supplemental analysis will be performed for PP(Per protocol) and As treated group. The primary endpoint will be concluded as 'noninferior' if both ITT and PP analyses confirm the noninferiority.

ITT group includes all study population. PP group is constituted from the ITT group after excluding the patients with major violation of the study protocol.

The null hypothesis was that the Avalus™ was inferior to the CEPME based on the AVMPG at 1-year echocardiographic follow-up, with a non-inferiority margin of 3mmHg. The result for the primary endpoint was presented with 97.5% one-sided confidence interval for mean difference between groups. The non-inferiority test was performed using a t-test which compared mean difference between groups with the non-inferiority margin under the one-sided significance level of 0.025.

For analysis of 1-year clinical outcomes including all-cause mortality, cardiac death, and MAEs, events were counted at postoperative 1 year, and comparisons between the 2 groups were made using the chi-square test and Fisher's exact test. A P value of $< .050$ was considered statistically significant.

8) Schedules

- ① Study planning : October 1, 2018 – November 31, 2018
- ② Enrollment : January 1, 2019 (or after IRB approval) – June 30, 2022

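### The primary noninferiority t-test is valid but leaves out institution, the stratification factor, and BSA; a prespecified adjusted model could narrow the interval at almost no cost

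*SAP*

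**What the plan says.** The protocol (section 10, 7) Efficacy) and the SAP (statistical analysis paragraph after section 3) give the same primary test. In the SAP it reads "The non-inferiority test will be performed using a t-test which compares mean difference between groups with the non-inferiority margin"; in the protocol, "The non-inferiority test was performed using a t-test which compared mean difference between groups with the non-inferiority margin". The result is reported as a one-sided 97.5% confidence interval. Neither document names an adjusted or stratified model for any outcome, whether as primary or as sensitivity analysis. The only supplements are per-protocol and as-treated analyses.

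The design does use baseline information. The randomisation note in protocol section 10, 1) describes blocks of 4 and 6, "considering the institution as a stratification factor". Section 10, 2) lists "Demographics: age, sex, height, weight, BMI, BSA, diagnosis, operation name". The split between the two hospitals is not fixed in advance: "The subjects will be recruited competitively" (section 9, 4)).

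The sample size section states "Fifty-six patients in each group are needed to complete the study cohort", or 70 per arm after 20% dropout. The Efficacy section concludes noninferiority only "if both ITT and PP analyses confirm the noninferiority".

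**The concern.** The trial's conclusion turns on whether the upper confidence limit for the AVMPG difference falls below 3 mmHg. At 80% power the plan accepts a 20% chance of missing that target in a single analysis set even if all its assumptions hold, so the width of the interval matters.

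Two sources of precision are left unused.

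- **Institution.** Blocking within institution balances the arms on hospital. If the hospitals differ in AVMPG, the t-test still counts that difference as noise. Its standard error is then larger than the design warrants, and the test becomes somewhat conservative.
- **BSA.** It is recorded at baseline. If it predicts AVMPG, including it removes residual variance. If it does not, it brings nothing.

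The covariates have to be named before outcome data are seen, because adding them later would look selective.

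**Working it through.** **Inputs** (protocol section 9, 3)): SD 4.3 mmHg in each arm; means 12.6 and 11.9, so a true difference of 0.7; margin 3; one-sided alpha 0.025; power 80%; 1:1 allocation; 20% dropout. The distance from the assumed difference to the margin is 3 − 0.7 = 2.3 mmHg.

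**Step 1: reproduce the plan's figure.** The stated formula gives n = (1.960 + 0.842)² × 2 × 4.3² / 2.3² = 54.9, so 55. With the t distribution, power is 79.4% at 55 and 80.1% at 56, so 56 per arm is right. Then 56 / 0.80 = 70.

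**Step 2: precision of the planned t-test at 56 per arm.** SE = 4.3 × √(2/56) = 0.813. With 110 df the critical value is 1.982, so the distance from estimate to limit (half-width) is 1.982 × 0.813 = 1.61 mmHg. Power is 80.1%.

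**Step 3: institution only.** The residual SD is 4.3 × √(1 − R²) with 109 df. No chance-imbalance penalty is charged because the blocks are stratified. R² is not in the documents, so the values are assumptions.

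| Site R² | Half-width (mmHg) | Power |
|---|---|---|
| 0 | 1.611 | 80.1% |
| 0.05 | 1.570 | 82.1% |
| 0.10 | 1.528 | 84.1% |

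In simulation the half-widths cross at a site R² of about 0.002. With equal sites that is a site difference of 2 × 4.3 × √0.002 = 0.38 mmHg.

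**Step 4: institution plus BSA.** With 108 df, the variance is multiplied by 1 + 1/(2n − 5) = 1 + 1/107 for chance imbalance in BSA. SE = 4.3 × √(1 − R²) × √((2/56)(1 + 1/107)).

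| Joint R² | SE | Half-width (mmHg) | Power | Completers per arm for 80% |
|---|---|---|---|---|
| 0 | 0.816 | 1.618 | 79.7% | 57 |
| 0.05 | 0.796 | 1.577 | 81.7% | 54 |
| 0.10 | 0.775 | 1.535 | 83.7% | 51 |
| 0.20 | 0.730 | 1.447 | 87.7% | 46 |

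The half-width equals that of the t-test at R² of about 0.01. Charging the imbalance penalty to institution as well gives 79.4% power at R² = 0 and break-even near 0.02.

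**Step 5: simulation.** 140 patients were randomised in blocks of 4 and 6 within two sites, with 20% random dropout and 112 completers (20,000 runs per setting). Both methods were applied to the same data. Power, t-test v institution plus BSA:

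| Scenario | Equal sites | 70:30 sites |
|---|---|---|
| Site R² 0.10 only | 81.5% v 84.1% | 80.3% v 82.9% |
| BSA R² 0.10 only | 79.9% v 83.4% | 80.3% v 83.7% |
| Site 0.05 plus BSA 0.10 | 80.3% v 85.5% | 80.8% v 85.6% |

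The adjusted interval was narrower in 23% of trials when both covariates explained nothing, and in about 96% at R² 0.10 from either one.

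**Step 6: type I error at a true difference of 3 mmHg.** For the t-test it was about 0.022 at site R² 0.05 and about 0.020 at 0.10 (Monte Carlo SE about 0.001). With perfect balance, P(Z > 1.96/√(1 − R²)) gives 0.022 and 0.019. For the adjusted model it was 0.023 to 0.027 over 16 settings.

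**The case against.** The case for leaving the plan alone is that nothing in it is wrong. The sample size and the test agree with each other, the test is valid, and being conservative is the safe direction for a noninferiority claim. All of that stands, and it is why this is a recommendation and not a required correction.

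The benefit also rests on an R² that the documents do not give, and they give no reason to prefer BSA over other recorded baseline variables. That stands too, so the gain is conditional. It does not remove the asymmetry: under one point of power is lost if the covariates are useless, and about 3.6 to 7.6 points are gained at R² 0.10 to 0.20.

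The larger site scenarios imply large differences between the hospitals. With equal sites, R² 0.05 means 2 × 4.3 × √0.05 = 1.9 mmHg and R² 0.10 means 2.7 mmHg; at 70:30, 0.10 means about 3.0 mmHg, as large as the margin. Nothing in the documents suggests differences of that size, so those rows are better read as an upper range. The case for institution does not need them, because including it costs about 0.01 points of power if it explains nothing.

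Finally, these power figures describe one analysis set, whereas success needs both ITT and PP. If PP drops about 5% of patients (an assumption), joint success under the planned t-test is about 75%. This lowers the baseline but does not weaken the argument: the adjusted model gains about as much under the joint rule when BSA is prognostic.

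**Conclusion.** The point holds as a low-cost improvement. The planned t-test is valid and reaches its stated power for a single analysis set, but it ignores the factor by which patients are randomised and a baseline variable already collected. Adding institution aligns the standard error with the stratified design at negligible cost, whatever BSA does. Adding BSA pays only if it is prognostic.

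At 56 completers per arm, the effect of including both ranges from a loss of 0.4 points of power at R² = 0 to gains of 1.6, 3.6 and 7.6 points at R² = 0.05, 0.10 and 0.20. These results assume the plan's SD, difference and dropout, and dropout unrelated to outcome. The R² values and site splits are assumptions. The size of any real gain is therefore unknown; the bound on the loss is much firmer.

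**What to change.** Before outcome data are seen, name as the primary analysis in the SAP and in the protocol's Efficacy section a linear model for 1-year AVMPG with treatment, institution and BSA (continuous). Compare the upper limit of the one-sided 97.5% confidence interval for the adjusted treatment difference with 3 mmHg, and apply this in both the ITT and PP sets. Leave the margin, alpha and hypotheses as they are. Keep the unadjusted t-test as a named sensitivity analysis.

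Fix the covariate list completely. Valve size is a tempting addition, since the candidate sizes for both "prostheses are decided before randomization", but size is not named among the operative data and an optional term would bring back the flexibility that prespecification removes. It is better left out. The label size of the valve actually implanted should not be used in any case, because it is settled only once the prosthesis has been assigned.

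The cost is wording in two documents, with no extra patients, procedures or data fields. The downside is a fall in power from 80.1% to 79.7% if neither covariate predicts AVMPG.
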